# CONFIDENTIAL UNIVERSITY OF NORTH CAROLINA

#### 7.1.2 Suspected Adverse Reaction (SAR)

A suspected adverse reaction (SAR) is any AE for which there is a *reasonable possibility* that the drug is the cause. *Reasonable possibility* means that there is evidence to suggest a causal relationship between the drug and the AE. A suspected adverse reaction implies a lesser degree of certainty about causality than adverse reaction, which means any adverse event caused by a drug. Each SAR will be graded on a mild-moderate-severe scale.

Causality assessment to a study drug is a medical judgment made in consideration of the following factors: temporal relationship of the AE to study drug exposure, known mechanism of action or side effect profile of study treatment, other recent or concomitant drug exposures, normal clinical course of the disease under investigation, and any other underlying or concurrent medical conditions. Other factors to consider in considering drug as the cause of the AE:

- Single occurrence of an uncommon event known to be strongly associated with drug exposure (e.g., angioedema, hepatic injury, Stevens-Johnson Syndrome)
- One or more occurrences of an event not commonly associated with drug exposure, but otherwise uncommon in the population (e.g., tendon rupture); often more than one occurrence from one or multiple studies would be needed before the sponsor could determine that there is *reasonable possibility* that the drug caused the event.
- An aggregate analysis of specific events observed in a clinical trial that indicates the events occur more frequently in the drug treatment group than in a concurrent or historical control group

#### 7.1.3 Unexpected AE or SAR

An AE or SAR is considered unexpected if the specificity or severity of it is not consistent with the applicable product information (e.g., Investigator's Brochure (IB) for an unapproved investigational product or package insert/summary of product characteristics for an approved product). Unexpected also refers to AEs or SARs that are mentioned in the IB as occurring with a class of drugs or as anticipated from the pharmacological properties of the drug, but are not specifically mentioned as occurring with the particular drug under investigation.

#### 7.1.4 Serious AE or SAR

An AE or SAR is considered serious if, in the view of either the investigator or sponsor, it results in any of the following outcomes:

- Death
- Is life-threatening (places the subject at immediate risk of death from the event as it occurred)
- Requires inpatient hospitalization (>24 hours) or prolongation of existing hospitalization

#### CONFIDENTIAL UNIVERSITY OF NORTH CAROLINA

- Results in congenital anomaly/birth defect
- Results in a persistent or significant incapacity or substantial disruption of the ability to conduct normal life functions
- Important medical events that may not result in death, be life-threatening, or require hospitalization may be considered a serious adverse drug experience when, based upon appropriate medical judgment, they may jeopardize the patient or subject and may require medical or surgical intervention to prevent one of the outcomes listed in the definition. For reporting purposes, also consider the occurrences of pregnancy as an event which must be reported as an important medical event.

\*Hospitalization for anticipated or protocol specified procedures such as administration of chemotherapy, central line insertion, metastasis interventional therapy, resection of primary tumor, or elective surgery, will not be considered serious adverse events.

Pregnancy that occurs during the study must also be reported as an SAE.

#### 7.2 Documentation of non-serious AEs or SARs

For non-serious AEs or SARs, documentation must begin from day 1 of study treatment and continue through 24 hours after treatment is discontinued.

Collected information should be recorded in the Case Report Forms (CRF) for that patient. A description of the event, its severity or toxicity grade, onset and resolved dates (if applicable), and the relationship to the study drug will be documented.

#### 7.3 SAEs or Serious SARs

#### 7.3.1 Timing

For any experience or condition that meets the definition of an SAE or a serious SAR, recording of the event must begin from day 1 of study treatment and continue through the 30-day follow-up period after treatment is discontinued.

#### 7.3.2 Documentation and Notification

These events (SAEs or Serious SARs) must be recorded within 24 hours of learning of its occurrence.

#### 7.3.3 Reporting

#### **IRB Reporting Requirements:**

- UNC will submit an aggregated list of all SAEs to the UNC IRB annually at the time of study renewal according to the UNC IRB policies and procedures.
- The UNC-IRB will be notified of all SAEs that qualify as an Unanticipated Problem as per the UNC IRB Policies using the IRB's web-based reporting system (see section 9.4.3) within 7 days of the Investigator becoming aware of the problem.

### CONFIDENTIAL UNIVERSITY OF NORTH CAROLINA

#### Pregnancy

Pregnancies and suspected pregnancies (including a positive pregnancy test regardless of age or disease state) of a female subject occurring while the subject is on study should be recorded as SAEs. The patient is to be discontinued immediately from the study. The female subject should be referred to an obstetriciangynecologist, preferably one experienced in reproductive toxicity for further evaluation and counseling.

The Investigator will follow the female subject until completion of the pregnancy, and must document the outcome of the pregnancy (either normal or abnormal outcome). If the outcome of the pregnancy was abnormal (e.g., spontaneous or therapeutic abortion), the Investigator should report the abnormal outcome as an AE. If the abnormal outcome meets any of the serious criteria, it must be reported as an SAE.

#### FDA Expedited Reporting requirements for studies conducted under an IND:

If an investigator deems that an event is both a serious SAR AND unexpected, it must also be recorded on the MedWatch Form 3500A as per 21 CFR 312.32. The MedWatch 3500a form can be accessed at:

http://www.fda.gov/Safety/MedWatch/HowToReport/DownloadForms/default.ht m. (Please be sure and access form 3500a, and not form 3500). For Affiliate Investigators, the MedWatch form should be faxed to the UNC Study Coordinator at [contact] along with supporting documentation defining the event and causality. UNC, as the Sponsor of the study, will make the final determination regarding FDA submission.

Once the UNC Principal Investigator determines an event is a serious SAR AND unexpected, the MedWatch 3500A form will be submitted to the FDA.

The UNC Study Coordinator will also be responsible for informing each Affiliate site of all serious and unexpected SARs reported to the FDA via fax as soon as possible.

#### 7.4 Data and Safety Monitoring Plan

The Principal Investigator will provide continuous monitoring of patient safety in this trial.

Every 2 weeks or more often as necessary, the UNC research team (including a minimum of PI and study coordinator) will meet to discuss enrollment, study-wide safety data, and logistical issues related to the study. Formal study meetings will happen every 6 months, during accrual, and include PI, study coordinator, nursing staff, sonographers, and any other relevant personnel. In addition, meetings/teleconferences will be held at a frequency dependent on accrual, at a minimum of every month, which will include the UNC and Affiliate investigators as

well as protocol nurses, study coordinators, regulatory associates, data managers, biostatisticians, and any other relevant personnel the principal investigators may deem appropriate. At these meetings, the research team will discuss *all issues relevant to study progress, including enrollment, safety, regulatory, data collection, etc.* 

The Study Coordinator will produce summaries or minutes of the UNC and Affiliate meetings. These summaries will be available for inspection when requested by any of the regulatory bodies charged with the safety of human subjects and the integrity of data including, but not limited to, the oversight (Office of Human Research Ethics (OHRE) Biomedical, or the North Carolina TraCS Institute Data and Safety Monitoring Board (DSMB).

Since this is not a randomized, blinded trial, enrollment with the Data Safety Monitoring Board would not provide added benefit to the patients. If during the course of the trial any of the Investigators feel the participation of the Data Safety Monitory Board (DSMB) would be of value, their assistance will be solicited.

#### 7.4.1 Monitoring Safety of Participants

Blood and urine test results within 8 weeks of study recruitment will be obtained from the subject's clinical provider at the time of enrollment, as a part of the standard of care disease management and for determination of inclusion. In particular, serum creatinine and any evidence of hematuria will be noted. Urinalyses will be obtained just prior and post-CEUS to detect any evidence of hematuria. Serum creatinine measurements and urinalyses will be followed during the duration of study follow-up with intervals at the discretion of the primary provider. This information will be compiled by study coordinators by review of the medical chart and when necessary, obtaining records directly from the clinical provider.

Multi-center safety issues and protocol changes will be communicated directly from Affiliate PI to the UNC PI and the research coordinators and recorded as in 7.2 and 7.3.3.

#### 7.4.2 Individual Subject Stopping

Patient safety will be considered during the study intervention with individual patient withdrawal for criteria outlined in 4.4 and managed as described in 4.6. There are no subsequent interventions after the initial contrast-enhanced ultrasound.

#### 7.4.3 Study-wide Stopping

If there is a severe SAR or a severe AE suspected to be related to the study intervention, CEUS, the study will be put on hold and re-evaluated as this would not be an expected event.

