#### CONFIDENTIAL UNIVERSITY OF NORTH CAROLINA

#### 7.4.4 Ensuring data accuracy and protocol compliance

The PI will monitor the accruing data and make decisions about the ongoing safety of the trial. A Medical Monitor outside the study will be asked to provide an independent review of the study and data. The UNC PI will be responsible for providing the following information for such a review: 1) safety and accrual data including the number of patients treated; 2) significant developments reported in the literature that may affect the safety of participants or the ethics of the study; 3) preliminary diagnostic data; and 4) summaries of team meetings that have occurred since the last report.

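### The mandatory study-wide hold depends on a severe grade and not on seriousness, and the outside Medical Monitor has no event-triggered or restart role

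*Combined protocol and SAP*

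**What the plan says.** **The hold.** Section 7.4.3 sets the trigger and the action in these words: "a severe SAR or a severe AE suspected to be related to the study intervention, CEUS, the study will be put on hold". The next step and the reason for it come after that: the trial is to be "re-evaluated as this would not be an expected event". It does not say who carries out the re-evaluation or who approves restart.

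**The grade.** Section 7.1.2 states "Each SAR will be graded on a mild-moderate-severe scale", and 7.1.1 does the same for AEs. Neither section defines the three grades.

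**Seriousness.** Section 7.1.4 defines this by outcome. Besides death and threat to life, it includes an event that "Requires inpatient hospitalization (>24 hours) or prolongation of existing hospitalization". It also covers important medical events that meet none of those outcomes when, in the clinician's view, "they may jeopardize the patient or subject and may require medical or surgical intervention to prevent one of the outcomes listed in the definition".

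**What a serious event sets in motion.** It "must be recorded within 24 hours of learning of its occurrence" (7.3.2). Under 7.3.3 it goes to the IRB within 7 days if it is an Unanticipated Problem and otherwise on an annual list. It goes to the FDA if it is both a serious SAR and unexpected.

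**Oversight.** Section 7.4.4 states "The PI will monitor the accruing data and make decisions about the ongoing safety of the trial". On outside review, the same section adds: "A Medical Monitor outside the study will be asked to provide an independent review of the study and data". The PI supplies a four-item package for that review, starting with safety and accrual data. Section 7.4 provides for team meetings at least every two weeks and lets any investigator ask for the DSMB.

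**The concern.** The protocol defines severity and seriousness separately but ties its only mandatory pause to severity. A severe headache thought to be caused by the contrast would stop the study. A suspected reaction that keeps a patient in hospital for more than a day, but is graded moderate, need not.

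A serious suspected drug reaction is an event for which a look from outside the team, before the next patient is dosed, has most value. Here the grade alone decides whether a pause is required, the grades are undefined, and both the grading and the restart can be settled within the study team. This matters somewhat more because the study uses a mechanical index of up to 1.1 (4.2.4), while the labelling summarised in 5.7 says safety above 0.8 has not been evaluated.

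**Working it through.** The stopping rule contains no threshold or error rate, so there is no planned figure to reproduce. The check is mainly a comparison of text, followed by a short calculation of how often the case could arise.

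**Step 1. Cross the two definitions.**

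| Suspected CEUS reaction | Graded severe | Graded mild or moderate |
|---|---|---|
| Serious under 7.1.4 | Hold required | No hold required |
| Not serious | Hold required | No hold required |

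The gap is the top right cell. Fatal or life-threatening reactions would almost surely be graded severe, so the cell contains mainly events that are serious because of hospitalization or as important medical events.

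**Step 2. See whether another route closes the gap.**
- FDA (7.3.3): only if the serious SAR is also unexpected. No hold follows.
- IRB (7.3.3): 7-day notice only for Unanticipated Problems, otherwise an annual list. Enrolment is planned for about 6 months (8.2), so that list could arrive after the last patient is dosed.
- DSMB (7.4): only if an investigator asks.
- Medical Monitor (7.4.4): reviews safety data, but no schedule, triggering event or restart role is stated.
- PI (7.4 and 7.4.4): may pause at discretion.

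So a pause is possible by several routes, but none requires one.

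**Step 3. Size the case.** Inputs: n = 75 patients (8.2). All 75 are used because the allowance of 10 is for loss after dosing. The rate p is 1 to 3 serious events per 10,000 patients, from the large safety studies cited in 1.3.2 under cardiopulmonary reactions.

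Expected number = n × p. Chance of at least one = 1 − (1 − p)^n.

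- p = 0.0001: 75 × 0.0001 = 0.0075 expected; 1 − 0.9999^75 = 0.75%.
- p = 0.0003: 75 × 0.0003 = 0.0225 expected; 1 − 0.9997^75 = 2.2%.

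Section 4.2.4 allows a second infusion for patients with more than one lesion. If every patient took it and the risk applied per infusion (both assumptions, and the first is extreme), n = 150 gives 1.5% to 4.4%.

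These figures cover serious events of any grade. The share graded below severe is not given in the documents. The premarket count of 26 serious events in 1716 subjects (1.3.2) is not used as the rate, because it is not limited to suspected reactions and those described were mostly attributed to underlying disease.

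**The case against.** The strongest reply is that the existing rule is already cautious and little is left uncovered. One severe suspected event at either site stops the whole study, even if it is not serious. The agent is marketed, exposure is confined to one visit, and patients are observed for 30 minutes. The uncovered events are an unquantified part of something already rare. Severe may also simply be a slip for serious. Most of this stands and keeps the priority low. A slip would be a reason to correct the word, since the protocol defines the two terms differently.

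Four stronger readings are tempting, and the documents do not support them.

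- A reader might infer that dosing would continue after a serious reaction graded moderate. The text shows only that no pause is mandatory. The PI monitors safety continuously and may pause, and the team discusses safety at least every two weeks.
- A reader might infer that the Medical Monitor would never see such an event. Safety data are in the review package, so the event belongs in the next review. What is missing is a time or a trigger.
- A reader might infer from the closing words of 7.4.3 that a labelled reaction escapes the hold. Those words give a reason for the hold and set no condition on it.
- A reader might take the premarket discontinuations in 1.3.2, described as moderate, as examples of serious but moderate reactions. They usually resolved untreated within minutes or hours, so they do not show this.

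**Conclusion.** The point holds as a gap in a stated rule. Followed as written, 7.4.3 does not require a hold for a suspected reaction that is serious under 7.1.4 but graded below severe, and nothing gives the Medical Monitor a role triggered by an event or before restart.

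The size is small: a chance of about 0.7% to 2.2% of any serious event in 75 patients, of which the relevant events are an unknown fraction. This assumes that the cited rate carries over and that the risk is per patient. The cited rate does not come from patients with kidney disease imaged at a high mechanical index, so the true figure could differ. It also rests on a judgment that the protocol's undefined grades would allow some hospitalized or promptly treated reactions to be called moderate. This is a worthwhile clarification of a safety rule and leaves the study's estimates untouched.

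**What to change.** In 7.4.3, change the trigger to: *a serious (as defined in 7.1.4) or severe SAR, or a serious or severe AE suspected to be related to CEUS*. Add one sentence: the Medical Monitor named in 7.4.4 reviews the event, and the review is documented, before enrolment resumes.

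The IRB and FDA routes stay as they are, and no DSMB or new committee is needed.

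The cost is about two sentences of protocol wording and an occasional review by someone the plan already provides for. The downside is a possible short pause in enrolment. With one infusion per patient, serious events would trigger a hold in about 2% of trials of this size or fewer at the cited rate, and some of those would be graded severe and held under the present rule anyway. Holds for severe but non-serious events would be no more frequent than now, but each would also wait for the Monitor's review.

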#### CONFIDENTIAL UNIVERSITY OF NORTH CAROLINA

#### 7.4.4 Ensuring data accuracy and protocol compliance

The PI will monitor the accruing data and make decisions about the ongoing safety of the trial. A Medical Monitor outside the study will be asked to provide an independent review of the study and data. The UNC PI will be responsible for providing the following information for such a review: 1) safety and accrual data including the number of patients treated; 2) significant developments reported in the literature that may affect the safety of participants or the ethics of the study; 3) preliminary diagnostic data; and 4) summaries of team meetings that have occurred since the last report.

#### **8.0 STATISTICAL CONSIDERATIONS**

#### 8.1 Study Design/Study Endpoints

This is an investigator-initiated, prospective pilot study evaluating the sensitivity of contrast enhanced ultrasound using microbubble contrast agent (perflutren lipid; Definity®) in diagnosing renal malignancy in patients with kidney disease and an indeterminate or possibly malignant kidney mass on a screening CT/MR/US. The study is designed to estimate the sensitivity of CEUS as a surrogate for conventional imaging.

#### 8.2 Sample Size and Accrual

This study will recruit to a target goal of 75 patients total between the primary site (UNC) and Affiliate (VU). We expect to complete the enrollment in about 6 months. Based on available literature regarding incidence of malignancy in indeterminate (Bosniak IIF and III) lesions and accuracy of CEUS for cystic kidney lesion characterization in a general, non-CKD population and our experience from a pilot study including 27 patients with kidney disease and an indeterminate lesion, we approximate a true positive rate of 10%, false positive rate of 8%, true negative rate of 80% and false negative rate of 2%. Given the sample size of 75 (allowing for 10 to be lost to follow-up/death) and these approximated rates, we project an achievable sensitivity of 83%, specificity of 91%, PPV of 56% and NPV of 98%. The 95% confidence interval for this sensitivity estimate is 74.5-91.5% with a width of 17%.

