#### CONFIDENTIAL UNIVERSITY OF NORTH CAROLINA

meet criteria. The PI will communicate with the patient's referring clinician and the patient to determine whether they fit the inclusion/exclusion criteria and would like to participate in the study. The study coordinator will then be notified of these patients and approach the patient to further explain the study and obtain their signature on the informed consent form if they wish to participate. If patients consents, they will undergo perflutren-enhanced US. We will make every attempt to perform the perflutren-enhanced US during a regularly scheduled clinic visit. We will provide \$50 compensation and a parking voucher for completion of initial CEUS study. If two lesions are imaged, they will receive \$100. We will offer an additional \$50 for completion of all follow-up studies (6-month and 1-year urinalysis and serum creatinine and 1-year follow-up conventional ultrasound) and \$75 if they are not cared for at UNC and need to make an additional trip to UNC to obtain the studies. We plan on enrolling a total of 75 patients that fit the above criteria over a 6-month period.

Healthy volunteers will also be recruited at study initiation to optimize the imaging technique. These volunteers will receive equivalent compensation. In the case of any abnormalities found during the study, the subject will be informed of the finding, and the finding will be communicated to the subject's primary provider by study PI for further management.

Patients that decline enrollment will be asked if they would be willing to participate as controls. This would involve no CEUS study and only collection of serum creatinine levels over a 1-year follow-up period from the patient's primary provider.

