#### CONFIDENTIAL UNIVERSITY OF NORTH CAROLINA

Similarly, other patient clinical and demographic characteristics will be summarized, using frequencies in the case of categorical variables.

For Aim 1, sensitivity and specificity and their 95% confidence intervals will be computed for CEUS qualitative interpretations compared to change in baseline noncontrasted US. Based on the gold standard diagnosis of lesion progression at one vear follow-up, a 95% confidence interval for the Mantel-Haenszel odds ratio will be constructed to quantify the odds that a subject with a diagnosis of a malignant lesion by non-contrasted US will be diagnosed with a malignant lesion by CEUS relative to the odds for a subject without a malignant lesion diagnosis by non-contrasted US. A similar odds ratio and 95% confidence interval will be constructed for subjects with a gold standard diagnosis of stable or lesion regression. Sensitivities, specificities are based on diagnoses made using CEUS-based risk classification (class I, II, and IIF considered negative, class III and IV as positive, using modified Bosniak criteria). Estimation of sensitivity and specificity will be carried out for each reader, two per site. Agreement between readers will be based on kappa statistics for the dichotomous diagnosis and using weighted kappas based on the ordinal Bosniak scale. Inter-institutional agreement will be assessed using kappa statistics by sending all decoded images from UNC to Vanderbilt and vice versa.

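### The projected 95% confidence interval for sensitivity divides by all 75 patients instead of the 8 or 9 expected truth-positives, so it is about three times too narrow

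*Combined protocol and SAP*

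**What the plan says.** Section 8.2 sets the target: "This study will recruit to a target goal of 75 patients total between the primary site (UNC) and Affiliate (VU"). Section 4.2.1 repeats the total of 75. For accuracy, section 8.2 assumes: "we approximate a true positive rate of 10%, false positive rate of 8%, true negative rate of 80% and false negative rate of 2" percent. It continues: "Given the sample size of 75 (allowing for 10 to be lost to follow-up/death"), and from this projects sensitivity 83%, specificity 91%, PPV 56% and NPV 98%. It closes with the precision statement: "The 95% confidence interval for this sensitivity estimate is 74.5-91.5% with a width of 17" percent.

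Section 4.2.6 defines a positive on the truth standard as a lesion that has progressed on non-contrast ultrasound at one year. Section 8.3 commits to intervals in the analysis: "For Aim 1, sensitivity and specificity and their 95% confidence intervals will be computed for CEUS qualitative interpretations". It names no interval method, and it estimates sensitivity and specificity separately for each reader. Section 8.1 labels the study a pilot: "This is an investigator-initiated, prospective pilot study evaluating the sensitivity of" CEUS.

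**The concern.** A half-width of 8.5 points around 83% is far tighter than a study of this size can give for a condition assumed to be present in 12% of patients. The denominator of sensitivity is the truth-positives, and the plan's rates leave very few of them.

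This interval is the only statement of precision in the plan, and it concerns a primary estimate. A reader of section 8.2 would conclude that 75 patients fix sensitivity to within about 9 points either way. If the denominator is wrong, the study could not tell a sensitivity near 50% from one near 95%, and nothing in the plan would warn of that.

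**Working it through.** **Inputs, all from section 8.2.** Enrolled 75; losses 10; TP 10%, FP 8%, TN 80%, FN 2%; projected sensitivity 83%; confidence level 95%.

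**1. What the four rates are.** They sum to 100% and reproduce every projected measure, so they are shares of the whole sample:
- sensitivity 10/(10+2) = 83.3%
- specificity 80/(80+8) = 90.9%
- PPV 10/(10+8) = 55.6%
- NPV 80/(80+2) = 97.6%

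**2. The plan's own interval.** Wald: p ± 1.96·√(p(1−p)/n). With p = 0.83 and n = 75, √(0.83 × 0.17/75) = 0.0434 and the half-width is 0.085. The interval is 74.5% to 91.5%, width 17.0 points, which matches the text exactly. Solving back, n = 1.96² × 0.83 × 0.17/0.085² = 75.0. Other choices do not match: Wald with n = 65 gives 73.9-92.1%, and Wilson or exact limits with n = 75 start near 73%. The denominator used was all 75 patients.

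**3. The right denominator.** Truth-positive share = 10% + 2% = 12%.
- 0.12 × 75 = 9.0 if nobody is lost
- 0.12 × (75 − 10) = 7.8 after the planned losses

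**4. Same formula, right denominator (p = 0.83).**
- n = 9: half-width 0.245, interval 58.5% to 107.5%, width 49 points, ratio 49.1/17.0 = 2.9
- n = 7.8: half-width 0.264, interval 56.6% to 109.4%, width 53 points, ratio 52.7/17.0 = 3.1

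**5. Intervals that stay within 0-100%, at whole counts near the projection.**

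| Detected / truth-positive | Exact (Clopper-Pearson) | Width | Wilson | Width |
|---|---|---|---|---|
| 6/8 | 34.9-96.8% | 62 | 40.9-92.9% | 52 |
| 7/8 | 47.3-99.7% | 52 | 52.9-97.8% | 45 |
| 7/9 | 40.0-97.2% | 57 | 45.3-93.7% | 48 |
| 8/9 | 51.8-99.7% | 48 | 56.5-98.0% | 41 |

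At exactly 83.3%, Wilson gives 48-96% (n = 7.8, width 48) and 51-96% (n = 9, width 45).

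**6. The count is itself random.** For a binomial with 65 patients and 12%, the 2.5th and 97.5th percentiles are 3 and 13 truth-positives.

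**7. What a 17-point width would take.** About 75 truth-positives: 75/0.12 = 625 evaluable patients, or 625 × 75/65 ≈ 721 enrolled at the plan's loss rate.

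**8. Specificity.** 88% of 65 is about 57 truth-negatives. With 52/57 correct, the exact interval is 81-97% and Wilson is 81-96%. The problem is confined to sensitivity.

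**The case against.** - **It is a pilot, and nothing depends on the figure.** No test, success threshold or stopping rule uses the projected interval, and the final intervals will come from the data, so the error does not reach the results. That is true and limits the harm. But the label excuses a small sample, not a wrong statement of what that sample will show.
- **Lesions, not patients, may be the unit.** Section 4.2.1 foresees more than one: "If two lesions are imaged, they will receive" a higher payment. The plan gives no lesion count. As an assumed upper case, two lesions in each of 65 patients, ignoring correlation within a patient, give 130 × 0.12 = 15.6 positives and a Wilson width of 36 points, still about twice the stated figure.
- **The 75 may already be net of losses.** The parenthesis is loosely worded, but 75 evaluable patients still yield only 9 positives.
- **The size depends on the method.** This stands in part. The factor of three compares Wald with Wald. Wilson at whole counts gives 2.4 to 3.1 times (8/9 to 6/8). The top exact figure, 3.6 times, is for 6/8, which is 75% rather than 83%. Since the number of positives could plausibly be anywhere from 3 to 13, any replacement interval is a projection and not a forecast. No method comes near 17 points.
- **Readers are analysed separately.** Pooling readings would add no truth-positives. If a reader's primary estimate used only images from that reader's own site, each estimate would rest on fewer than 8 positives and the corrected interval would itself be optimistic. This does not help the printed figure, but section 8.3 should settle it.

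**Conclusion.** The concern holds. The interval in section 8.2 is the Wald interval for 83% with all 75 enrolled patients as denominator. The section's own rates leave about 8 to 9 truth-positives, so the like-for-like width is 49 to 53 points, about three times the stated 17. Across exact and Wilson limits at 6/8 to 8/9 the width is roughly 41 to 62 points.

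This rests on the plan's assumed 12% truth-positive share, its allowance of 10 losses and one lesion per patient. Relaxing the last two does not rescue the figure. The projected precision for specificity, which the plan does not give, would be reasonable. Because the erroneous figure is the plan's only statement of precision and concerns a primary estimate, it must be corrected.

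**What to change.** In section 8.2, replace the precision statement with:
- the expected number of truth-positives: about 8 among 65 evaluable patients (95% range 3 to 13);
- the projected 95% interval for sensitivity: about 48-96% (Wilson at 83.3%, n = 7.8), with whole-count examples by the exact method, 35-97% for 6/8 and 47-99.7% for 7/8;
- the projected 95% interval for specificity: about 81-97% (exact, 52/57);
- a sentence saying that the sensitivity estimate is preliminary, in line with the pilot label in section 8.1.

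In section 8.3, name an exact or Wilson interval, since the Wald upper limit passes 100% at these counts, and say whether each reader's estimate uses images from both sites or only from that reader's own.

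The cost is wording, plus a much less favourable stated precision for sensitivity. The correction does not in itself require more patients. Whether a width of 45 points or more is acceptable for the study's purpose is for the sponsor to decide, with the 625-evaluable-patient figure in view.
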